9.1.4. Part E

In Part E, LY2157299 will be administered orally at 150 mg BID for 21 days followed by 7 days off. A cycle is defined as 28 days. Section 9.1.5.1 details the DLT criteria that will be used. [Table JBAK.6](#) shows the proposed dose level and schedule for Part E.

Table JBAK.6. Treatment Regimen for Part E

Dose	Schedule	Time of Day
LY2157299 150 mg BID	Daily by oral administration 21 days on/7days off	Morning and evening for 21 days and then paused for 7 days

Abbreviations: BID = twice daily.

9.1.5. Criteria for Dose Escalation (Parts C and D)

Dose escalation will be driven by safety using the 3+3 method. Both cohorts will have a minimum of 3 patients enrolled. If 1 patient in either dose level experiences a DLT within the first cycle of LY2157299 and sorafenib or ramucirumab, then up to 3 additional patients will be enrolled at that dose level. If a DLT is observed in 2 or more patients at either dose level in the first cycle, dose escalation will cease and either the previous dose level will be declared the maximum tolerated dose (MTD) or, following discussions between the sponsor and

investigators, additional patients may be treated at intermediate doses between the previous and current dose levels.

By nature of being a dose-escalation safety assessment, data will be evaluated on an ongoing basis until the MTD is determined, as defined in Section 9.1.5.1. The maximum dose of LY2157299 will be 150 mg BID. Safety data, in particular AEs, will be the primary criteria for the dose escalation. The dose will be escalated following assessment of toxicity using the standard scoring system, CTCAE version 4.0, established by the National Cancer Institute (NCI). Any AEs related to LY2157299 or sorafenib (Part C) or ramucirumab (Part D) will be considered as toxicities.

In addition, if available at the time of dose-escalation decision, PK (eg, maximum plasma drug concentration, area under the curve, and apparent systemic clearance) results will be used as secondary/supporting data for dose escalation.

Additional patients may be enrolled at a specific dose level to characterize PK/PD.

Intermediate doses levels will be explored if deemed necessary after discussion between the sponsor and investigators.

Inpatient dose escalation is not permitted and dose escalation to the next cohort cannot occur without prior discussion and agreement between the investigator and the responsible Lilly clinical research physician (CRP). The decision will be documented in writing.

9.1.5.1. Dose-Limiting Toxicity Determination and Maximum Tolerated Dose Definition (Parts C, D and E)

A DLT is defined as an AE during Cycle 1 in Cohorts 1 or 2 that is related to the LY2157299 and sorafenib combination regimen in Part C, to the LY2157299 and ramucirumab combination regimen in Part D, or to LY2157299 administered on a 21 days on / 7 days off schedule in Part E and fulfills any 1 of the following criteria using NCI CTCAE v 4.0:

- \geq CTCAE Grade 3 nonhematological toxicity. Exceptions will be made for:
 - Nausea, vomiting, constipation, diarrhea \leq 72 hours, or electrolyte disturbance that can be controlled with treatment or optimal supportive care
 - Transient (<7 days) Grade 3 elevations of ALT and/or AST, without evidence of other hepatic injury, in the setting of preexisting hepatic metastasis may not be considered a DLT if agreed by the study investigator and Lilly CRP/clinical research scientist
 - Hand-foot syndrome attributed to sorafenib only
 - Hypertension attributed to sorafenib or ramucirumab only that cannot be adequately controlled
- CTCAE Grade 4 hematological toxicity of >5 days duration
- Any febrile neutropenia

- Grade 3 or 4 thrombocytopenia with bleeding
- Any other significant toxicity deemed by the primary investigator and Lilly clinical research personnel to be dose limiting (for example, any toxicity that is possibly related to the combination regimen that requires the withdrawal of the patient from the study during Cycle 1)

As a guidance of toxicity relationship for sorafenib, please refer to [Attachment 16](#) (safety profile for sorafenib).

For the purpose of this study, the MTD is defined as the highest tested dose in each part that has <33% probability of causing a DLT during Cycle 1.

As patients receive more cycles of treatment, investigators, together with the Lilly CRP, can declare a DLT-equivalent toxicity if a patient is experiencing increasing toxicity during treatment in later cycles (ie, other than Cycle 1), and it becomes clear that it will not be possible to complete the treatment without exposing the patient to excessive risk.

Once the MTD has been defined, that dose level will be expanded in Parts C, D and E.

If toxicities are observed in the first cycle that would meet the DLT criteria defined above for Cohorts 1 and 2 or DLT-equivalent toxicities occur in 33% or more of patients within the cohort expansions in Part C, D and E, then investigators and the Lilly CRP will assess the nature and severity of these toxicities. The safety review and decision will be documented in writing.

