5.1.5.2. JBAK: Brief Summary of Results to Date

At the time of Amendment (e), Part A and Part B of the study have completed. A total of 149 patients were enrolled (109 in Part A and 40 in Part B). Eighty-five percent of patients were male and the median age was 65 years. Fifty-six percent of patients had an ECOG performance status (PS) of 0 and 44% had a PS of 1. Eighty-six percent of patients had a Child-Pugh Class A score and 14% had a Class B score. Etiology of disease was as follows: hepatitis C 24%, hepatitis B 20%, alcohol 20%; multiple 9.4%. Overall, 83% of patients had received prior sorafenib. Eleven patients discontinued treatment due to AEs: 8 were considered related to study treatment. Grade 3/4 AEs possibly related to treatment were observed in 26 (17%) patients. Of these AEs, neutrophil count decrease was observed in 4 patients. Anemia, hypoalbuminemia, decreased bilirubin, fatigue and embolism were observed in 2 patients each. All other AEs occurred in just 1 patient. Median TTP was 11.9 weeks (95% CI: 6.3, 12.6) in Part A and 18.0 weeks (95% CI: 10.0, 24.0) in Part B. Median OS was 31.4 weeks (95% CI: 22.9, 40.6) in Part A and 73.0 weeks (95% CI: 45.4, 104.7) in Part B. The median OS for the overall population was estimated as 40.4 weeks (95% CI: 31.1, 52.4) (Giannelli et al. 2016).

Enrollment into Part C has completed and maturation of the data is awaited. Enrollment is ongoing in Part D of the study.

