- Two treatment groups: LY2157299 80 mg BID on Days 1 to 14 in combination with sorafenib at 400 mg BID on Days 1 to 28 versus LY2157299 150 mg BID on Days 1 to 14 in combination with sorafenib at 400 mg BID on Days 1 to 28. Both cohorts were to be on a 28-day cycle.

Patients enrolled in the safety lead-in cohorts were to continue treatment as per that cohort.

[figure not shown]

Figure JBAK.2. Illustration of study design for Protocol H9H-MC-JBAK Part C.

[figure not shown]
Part D

Part D will be conducted outside of the EU and will evaluate LY2157299 in combination with ramucirumab in patients with advanced HCC and Child-Pugh Class A status. Part D comprises 2 cohorts (Figure JBAK.3). Patients enrolled in Cohort 1 will be administered LY2157299 80 mg BID on Days 1 to 14 in combination with ramucirumab administered at 8 mg/kg as an intravenous (IV) infusion on Days 1 and 15 of every cycle. Approximately 18 patients may be enrolled to allow the selected dose to be expanded to approximately 15 patients in total.

Three patients will be initially enrolled on Cohort 1; if no dose-limiting toxicities (DLTs) (related to LY2157299 or the combination regimen) are observed in Cycle 1, then 3 patients will be treated on Cohort 2 at LY2157299 150 mg BID on Days 1 to 14 in combination with ramucirumab 8 mg/kg administered as an IV infusion on Days 1 and 15 of every cycle. If a DLT related to LY2157299 or the combination regimen is observed in the first 3 patients in Cycle 1 of Cohort 1, Cohort 1 will enroll an additional 3 patients. If no further DLTs are observed, Cohort 2 will be opened. If 1 or more additional DLTs are observed in Cohort 1, Part D will close. If Cohort 2 is opened and no DLTs are observed in the first 3 patients, Cohort 2 will be expanded until approximately 15 patients have been enrolled. If 1 DLT is observed in Cycle 1 in the first 3 patients in Cohort 2, another 3 patients will be enrolled. If 2 or more DLTs are observed in the first 3 patients OR 1 or more DLTs are observed in the additional 3 patients in Cohort 2, a safety review by Lilly and the investigators will occur to decide whether to expand Cohort 1. If no further DLTs are observed in Cohort 2, Cohort 2 will be expanded until a total of approximately

15 patients have been enrolled at this dose. See Section 9.1.5 for more detailed dose escalation and expansion criteria.

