- [23] Have a history of any other cancer (except nonmelanoma skin cancer or carcinoma in situ of the cervix) unless in complete remission and off all therapy for that disease for a minimum of 3 years.
- At the discretion of the investigator, hormone-refractory prostate cancer patients who are stable on GnRH agonist therapy and breast cancer patients who are stable on antiestrogen therapy (for example, an aromatase inhibitor) may have that treatment continued while they are enrolled in this study.
- [24] Have active infection that would interfere with the study objectives or influence study compliance.
- [25] For Part C, have a known hypersensitivity to sorafenib or its excipients.
- [26] For Part D, have a serious illness or medical condition(s), including but not limited to the following:

- a) The patient has undergone major surgery within 28 days prior to randomization or has undergone central venous access device placement within 7 days prior to randomization.
- b) The patient has uncontrolled arterial hypertension $\geq 150 / \geq 90$ mm Hg despite standard medical management.
- c) The patient is receiving ongoing therapy with nonsteroidal anti-inflammatory agents (NSAIDs) (eg, indomethacin, ibuprofen, naproxen, nimesulide, celecoxib, etoricoxib, or similar agents) or other antiplatelet agents (eg, clopidogrel, ticlopidine, prasugrel, dipyridamole, picotamide, indobufen, anagrelide, triflusal, or similar agents). Aspirin at dosages up to 100 mg/day is permitted.
- d) The patient is receiving therapeutic anticoagulation with warfarin, low-molecular-weight heparin, or similar agents. Patients receiving prophylactic, low-dose anticoagulation therapy are eligible provided that the coagulation parameters defined in the inclusion criteria are met.
- e) Uncontrolled thrombosis (including myocardial infarction, unstable angina, cerebrovascular accident, or transient ischemic attack within 6 months prior to randomization) or bleeding.

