	No improvement within 7 days or 2nd or 3rd occurrence	Interrupt sorafenib treatment until toxicity resolves to Grade 0-1. When resuming treatment, decrease sorafenib dose by 1 dose level (400 mg daily or 400 mg every other day)
	4th occurrence	Discontinue sorafenib treatment
Grade 3: Moist desquamation, ulceration, blistering or severe pain of the hands or feet, or severe discomfort that causes the patient to be unable to work or perform activities of daily living	1st or 2nd occurrence	Interrupt sorafenib treatment until toxicity resolves to Grade 0-1. When resuming treatment, decrease sorafenib dose by 1 dose level (400 mg daily or 400 mg every other day)
	3rd occurrence	Discontinue sorafenib treatment

Source: FDA, 2011 (sorafenib prescribing information).

Suggested Management of Hypertension (adapted from Izzedine et al. 2009)

- Blood pressure should be checked regularly on sorafenib therapy. Hypertension should be managed in accordance with standard medical practice for sorafenib individualized to the patient's clinical circumstances (refer to local institutional guidance, other available guidelines, or Izzedine et al. 2009).
- For hypertension $>140/90$ and $\leq 160/100$: Continue sorafenib. Consider adding or adjusting anti-hypertensive medications.
- For persistent ($>160/100$) or symptomatic hypertension: Interrupt sorafenib. Resume when blood pressure improves to $\leq 160/100$. If persistent hypertension with optimal treatment consider decrease sorafenib by 1 dose level.
- In case of hypertension crisis (Grade 4), sorafenib should be withheld.

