9.5.3.2. Hypertension

Monitor blood pressure during treatment with ramucirumab and treat as clinically indicated. Temporarily suspend ramucirumab for severe hypertension until controlled with medical management.

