10.2.4. Echocardiograms with Doppler and Chest CT Scans

Because of the cardiotoxicity monitoring in this study, echocardiographs with Doppler and chest CT scans are being performed (see [Attachment 1](#), [Attachment 12](#), and [Attachment 13](#)).

Echocardiography with Doppler will be locally assessed at screening for enrollment and throughout the study according to the Study Schedule ([Attachment 1](#)) for safety decisions by a physician or a person who is qualified by experience or training. The individual must be identified at each site. A central reading will be performed for the data used in the study report.

Chest CT scan with contrast of thorax and abdomen to evaluate the large vessels of the heart will be locally assessed at screening for enrollment and throughout the study according to the schedule of events ([Attachment 1](#)) for safety decisions by a physician or a person who is qualified by experience or training. Alternatively, chest and/or abdomen MRI are allowed.

If the patient has clinically significant cardiac findings at discontinuation (Visit 801), echocardiography, ECG and ECG chemistry will be repeated every 2 months for 6 months (Visits 803, 804, and 805).

If there are no clinically significant cardiac findings at discontinuation (Visit 801), 1 more echocardiography, ECG, and ECG chemistry will be performed after 2 months (Visit 802). If a patient receives another treatment, Visit 802 cardiac assessments will not be performed.

The monitoring described in the above 2 paragraphs also applies to patients in the extension period. Therefore, for these cases, the patient does not discontinue from the study at the end of the 30-day follow-up period but after the cardiac findings have either resolved or, if not resolved after 6 months, after discussions between the Lilly CRP and investigator.

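### The hypertension exception in the DLT definition is the wrong way round, and the visit numbers for cardiac follow-up do not match the stated interval

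*Protocol*

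**What the plan says.** **DLT rule.** In Protocol 9.1.5.1 the sub-bullets under the Grade 3 or higher nonhematological criterion are events that do not count as DLTs. The first covers gastrointestinal events and electrolyte disturbance "that can be controlled with treatment or optimal supportive care". The last covers "Hypertension attributed to sorafenib or ramucirumab only that cannot be adequately controlled". Protocol 9.1.5 treats any adverse event related to LY2157299 or to the partner drug as a toxicity, and stops escalation at two DLTs in a cohort. For Part D Cohort 1, Section 7.1 adds three patients after one DLT in the first three, and then states: "If 1 or more additional DLTs are observed in Cohort 1, Part D will close". Section 5.1.5.2 reports that "Enrollment is ongoing in Part D of the study".

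**Cardiac follow-up.** Protocol 10.2.4 says that, for patients with clinically significant cardiac findings at Visit 801, echocardiography, ECG and ECG chemistry are "repeated every 2 months for 6 months (Visits 803, 804, and 805". Footnote b of the four study schedules in Attachment 1 (Parts A and B, C, D, and E) names the same visits. For patients without findings, Section 10.2.4 asks for one repeat after two months and calls it Visit 802. Section 10 sets Visit 802 and all later visits at 60-day intervals, with a window of 7 days either side.

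**The concern.** An exception to a DLT rule normally removes events that can be managed. This one removes the events that cannot be managed and leaves the manageable ones in the count. No sensible intent fits the wording. If manageable events were to be exempt, the verb should be positive, as in the first exception. If all partner-only hypertension were to be exempt, as hand-foot syndrome due to sorafenib is, no qualifier is needed.

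Elsewhere the protocol treats uncontrolled hypertension as the serious case. Exclusion criterion [26] b bars a Part D candidate when "The patient has uncontrolled arterial hypertension" despite standard management. Section 9.5.3.2 says "Temporarily suspend ramucirumab for severe hypertension until controlled with medical management". Section 9.5.2 says "In case of hypertension crisis (Grade 4), sorafenib should be withheld". At stake is whether a cohort escalates, expands or closes.

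In the follow-up rule, the interval and the visit numbers cannot both be followed. A site that schedules by visit number would give patients with significant cardiac findings their first planned repeat echocardiogram later than patients with none. Heart and great vessels are the main nonclinical target organs (Section 5.1.4), so this is the group that most needs the early check.

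**Working it through.** **1. DLT exception.** The documents give no hypertension rates, so the check traces the Part D Cohort 1 rule in Section 7.1:

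- 0 of 3 DLTs: Cohort 2 opens.
- 1 of 3: three more patients are enrolled.
- No further DLT (1 of 6): Cohort 2 opens.
- One or more further DLTs (2 or more of 6): Part D closes.

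Add one patient with Grade 3 or higher hypertension attributed to ramucirumab alone. In the first two rows one unrelated DLT has already occurred in the first three patients and the hypertension occurs among the next three. In the last two rows there is no other DLT and the hypertension occurs in the first three.

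| Other DLTs | Hypertension | Count as written | Decision as written | Count if corrected | Decision if corrected |
|---|---|---|---|---|---|
| 1 | controlled | 1 + 1 = 2 of 6 | Part D closes | 1 of 6 | Cohort 2 opens |
| 1 | uncontrolled | 1 of 6 | Cohort 2 opens | 1 + 1 = 2 of 6 | Part D closes |
| 0 | controlled | 1 of 3 | 3 more patients | 0 of 3 | Cohort 2 opens |
| 0 | uncontrolled | 0 of 3 | Cohort 2 opens | 1 of 3 | 3 more patients |

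The written rule gives the opposite decision in every row. Controlled events make it too strict and uncontrolled events make it too lenient. The net effect on the chance of clearing a cohort depends on the mix of the two, which the documents do not give.

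**2. Visit timing.** Inputs from Section 10: Visit 801 closes 30 days after treatment stops, and later visits are 60 days apart.

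Days after Visit 801 = 60 × (visit number − 801). Days after treatment stops = 30 + that figure.

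| Visit | Days after V801 | Approx. months after V801 | Days after treatment stops |
|---|---|---|---|
| 802 | 60 | 2 | 90 |
| 803 | 120 | 4 | 150 |
| 804 | 180 | 6 | 210 |
| 805 | 240 | 8 | 270 |

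Two-monthly testing for six months after Visit 801 needs days 60, 120 and 180, which are Visits 802, 803 and 804. The named visits give days 120, 180 and 240: the two-month test is missing and the last falls two months late. A window of 7 days cannot absorb a 60-day shift. Section 10.2.4 itself calls the two-month visit 802, which agrees with this grid.

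**Cross-check.** SAP 5.3.9.3 calls Visit 803 the two-month visit, which implies one month per visit number: (803 − 801) × 1 = 2. Its Visits 803, 805 and 807 then fall at 2, 4 and 6 months, which is coherent. The same times on the protocol's grid are again Visits 802, 803 and 804. The SAP supplied is aligned with Amendment (c), so this supports the finding but is not needed for it.

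**The case against.** The strongest reply is that both are drafting slips with obvious intent, that they are unrelated, and that safeguards limit the harm.

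On the DLT rule:

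- Part C enrollment is complete. The protocol does not say whether a 3+3 decision in Part D was still open at Amendment (e), so the table shows possible situations and not a known one. This stands.
- Escalation needs documented agreement between the investigator and the sponsor physician (9.1.5), and a discretionary criterion in 9.1.5.1 allows any other significant toxicity to be declared dose limiting. Both can rescue an uncontrolled event. Neither gives a stated ground for discounting a controlled event that the rule counts.
- Section 7.1 speaks of DLTs related to LY2157299 or the combination regimen, so it can be argued that partner-only events never count. But 9.1.5 includes partner-drug toxicity, and an exception for partner-only hypertension would be needless if such events were already outside the rule.
- Blood pressure is managed under 9.5.2 and 9.5.3.2 whatever the DLT label. This protects the individual patient but does not correct the cohort decision.

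On the visits:

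- The interval in words can be read as the operative instruction, and the spacing of the named visits is right. Only the start is shifted.
- Section 10 does not excuse missing information at Visit 802 when cardiac toxicity needing monitoring was seen at Visit 801. Footnote a of the schedules also requires follow-up about every 30 days for drug-related toxicity. These patients are therefore not unseen, but neither provision specifies an echocardiogram at two months.

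These points lower the likelihood of harm. They leave both stated rules wrong.

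**Conclusion.** Both points hold, and they are independent of each other. The DLT exception is the more serious because it is a decision rule: one partner-only Grade 3 or higher hypertension event in Cycle 1 can reverse whether Part D closes or escalates. Its reach is limited to hypertension attributed solely to sorafenib or ramucirumab in Parts C and D. Events attributed even partly to LY2157299 still count, and Part E has no partner drug. No overall probability can be given from the documents.

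The cardiac visit numbers are one visit late throughout. By number, the first planned repeat comes at about 120 days instead of 60 after Visit 801, against about 60 days for patients with no findings. This assumes that the 60-day grid in Section 10 applies and that the interval is counted from Visit 801, as the text in 10.2.4 indicates.

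The correction should be made before any further Part D cohort decision.

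**What to change.** 1. In Protocol 9.1.5.1, change cannot to can in the hypertension exception.
2. Check every Part C and Part D cohort decision in which Grade 3 or higher hypertension occurred in Cycle 1. Record whether the corrected rule would have changed it.
3. In Protocol 10.2.4 and in footnote b of all four schedules in Attachment 1, replace Visits 803, 804 and 805 with Visits 802, 803 and 804.
4. Align the visit numbers in SAP 5.3.9.3 if the current SAP version still differs.

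The cost is one word and three visit numbers in five places, by clarification letter or at the next amendment, plus a short review of past decisions. No new procedure is needed.

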9.2. Selection and Timing of Doses

Room-temperature storage condition is recommended for both the tablet drug products. The tablets should remain in the primary packaging until just prior to administration.

At the discretion of the investigator, if a patient vomits within 30 minutes of taking a dose of LY2157299, the LY2157299 dose should be repeated 1 time only that same day, if nausea/vomiting permits.

LY2157299 and sorafenib (for Part C) should be taken at approximately the same time every day. Patients should take the agent preferably 1 hour before breakfast and 1 hour before dinner.

For Part D and Part E, LY2157299 should be taken mornings and evening approximately 12 hours apart. Patients should take the agent preferably 1 hour before a meal.

In Part D, ramucirumab should be given in the mornings. On Day 1 of each cycle, LY2157299 should be taken within 30 minutes before the start of ramucirumab treatment.

Tablets should be swallowed whole and not split, crushed, or dissolved for administration.

